#### 9.4.8 TABULATION OF INDIVIDUAL PARTICIPANT DATA

Data will be tabulated as de-identified, without site or patient identifiers.

#### 9.4.9 EXPLORATORY ANALYSES

In exploratory analyses, we will examine the dose of intervention (total minutes; average minutes per week), and the degree of concordance between mentor and mentee characteristics as a mediator or moderator of the impact of the intervention.

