#### *Mentor PEER Phone Support*

Mentors will contact their mentees at least once a week for a total of 12 weeks. The mentees will also be given the option to contact their mentees should the need arise at any point during the 3-month intervention. Phone billing records will be reviewed to determine the total dose of intervention (call minutes with mentor) total for the period, monthly average, and weekly average. The distribution of the range of call duration for each mentee will also be described. A minimum of 3 minutes completed is required to count as a completed call.

Additional in-person, or video interactions between mentors and mentees will be self-reported by mentors in their contact logs, or as observed by study team during social mixers. These interactions will be included in the dose calculation of the intervention.

The quality of the mentor/mentee interactions will be evaluated using content analysis of recordings and the contact logs of mentors and mentees. Additional information of the quality will be evaluated by the study coordinator in the monthly or quarterly surveys of mentors and mentees.

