#### 6.4 STUDY INTERVENTION/EXPERIMENTAL MANIPULATION ADHERENCE

Adherence of mentees to the peer support intervention will be monitored by the research team including monthly surveys with the mentee asking about the calls with their mentors, as well as review of phone records (See Section 6.2.1). For mentees not participating in calls with mentor the study team will attempt to identify and address the barriers to participation. If pairs want to disengage, we will give the option of pairing with another mentor/mentee from the pool.

Attendance records and notes for participation in any social mixers (in-person or video) will also be maintained and reviewed for assessment of mentee participation in the intervention, including engagement with mentors.

Although all activities are intended and preferred, mentees will not be withdrawn for not participating in the intervention. They will be included in the primary study analysis as intention-to-treat. Secondary analyses may include an adjustment variable considering the dose delivered of the intervention.

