## 9.2 SAMPLE SIZE DETERMINATION

For evaluation of the primary endpoint, estimates are based on local dialysis unit hospitalization events in the past 12 months. For the control group, we expect 0.27 events per month (100 prevalent patients and 27 composite events per month). With 73 patients per group (after 25% drop-out), our study has >80% power to detect 20% reduction (i.e. a reduction of 0.054 visits per person-month) at type 1 error level 0.05. We will recruit at least 100 patients per group over the course of the study.

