## 9.4 STATISTICAL ANALYSES

### 9.4.1 GENERAL APPROACH

Descriptive statistics will be used to provide for each variable: number of observations, mean, standard deviation, median, minimum and maximum for continuous variables; frequencies and proportions for categorical variables. Results will be reported in accordance with the extended CONSORT guidelines for pragmatic clinical trials using two-sided statistical tests and confidences intervals. For all analyses, the overall level of significance will be set at 0.05. All analyses will be adjusted for site. Adjustment variables will be pre-specified in the following sections. All analyses will be performed using SAS v9.4 (SAS Institute, Cary, NC), STATA (College Station, Tx), or R (currently 3.6.1; <https://cran.r-project.org/>).

Analyses of qualitative data will include content analysis, novel code generations as applicable, interpretation and descriptive reporting.

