#### 9.4.2 ANALYSIS OF THE PRIMARY ENDPOINT(S)

##### ED Visit and Hospitalization Count

Each month all enrolled patients will be evaluated for ED visit or hospitalization encounters by both self-report and medical record review. The events will be tabulated each month up to an 18-month period of follow-up. The rates of the composite event will be determined as event per patient-month and compared between the intervention and usual care group using Poisson regression with two random intercepts. In the regression model, the composite counts of ED visits and hospitalization during up to 18-months follow-up is the outcome variable and the intervention assignment of the mentees is the primary binary predictor. The log of follow-up time will be included as offset. The random intercepts will account for the correlation between mentees who share a common mentor as well as the correlation between mentees who are from a common dialysis facility (out of seven facilities). As a randomized controlled trial, we do not anticipate the need for covariate adjustment. However, if evaluation of patient characteristics by group identifies a failure of randomization and imbalance in key characteristics as an example including age, gender, comorbidity, race, or dialysis vintage they will be considered as adjustment variables in the analysis. We will control for type 1 error at 0.05. An exploratory analysis will consider the comparison between the groups but at 3-months of observation after the conclusion of the intervention delivery.

We will perform residual analysis for the mixed effects models. For mixed effects models, we will examine marginal residuals to check linearity and within-subjects covariance matrix and conditional residuals to check outliers as well as normality and homoscedasticity of the residual errors. In case Pearson residual analyses indicate overdispersion in the Poisson mixed effects model, we will perform quasi-Poisson model. We will use robust sandwich estimator in the presence of misspecification of the covariance matrix (i.e. random effects structure).

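### Mentor call minutes are zero by design in every control, so dose cannot be an adjuster or moderator in the arm comparison, and without a stated time order and confounder set it can mislead

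*Combined protocol and SAP*

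**What the plan says.** - **Dose.** Section 6.1.2 (Mentor PEER Phone Support): "Phone billing records will be reviewed to determine the total dose of intervention (call minutes with mentor) total for the period". Mentors' self-reported in-person and video contacts are added to it. The intervention lasts 3 months.
- **Controls.** Section 6.1.1 gives the usual-care group printed material and their ordinary providers, and no mentor.
- **Outcome.** Section 9.4.2: "the composite counts of ED visits and hospitalization during up to 18-months follow-up is the outcome variable", with log follow-up time as offset. That section does not say when counting starts. The Synopsis does: the count includes the 3 intervention months. Observation is now 12 months, or 12 to 18 for those already enrolled.
- **Uses of dose.** Section 6.4: "Secondary analyses may include an adjustment variable considering the dose delivered of the intervention". Section 9.4.9: "we will examine the dose of intervention (total minutes; average minutes per week"), as mediator or moderator, alongside mentor/mentee concordance.
- **Not stated.** None of these places gives a model, a control-arm value for dose, a time order or a confounder set.
- **Related text.** Section 4.1 foresees exploratory work confined to the intervention arm. Sections 6.4 and 9.3 keep the primary analysis by intention to treat, whatever the dose received.

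**The concern.** Three features combine. Dose is measured after randomisation, has no variation in one arm, and is collected in months whose events are part of the outcome. The first two change what an arm comparison containing dose estimates, or make it inestimable. The third allows events to influence dose as well as dose to influence events.

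Section 2.3.2 presents measurement of intensity, frequency and duration as a basis for scaling the programme, so the dose results will be read as evidence on how much contact is needed. A trial with no effect could report that more minutes go with fewer admissions, next to an arm effect that looks harmful. This is separate from the as-treated regrouping in Section 9.3 and remains however that threshold is settled.

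**Working it through.** **1. Inputs from the documents.** Section 9.4.1: "For all analyses, the overall level of significance will be set at 0.05", "using two-sided statistical tests and confidences intervals". Section 9.2: "we expect 0.27 events per month" per control patient; a 20% reduction gives 0.27 x 0.80 = 0.216; 73 per group after 25% drop-out, at least 100 recruited. Sections 6.1.1 and 6.1.2: 12 weekly calls with a goal of 20 minutes, 12 x 20 = 240 minutes = 4 hours.

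**2. The plan's own figure.** Section 9.2 states "our study has >80% power to detect 20% reduction". With 73 x 18 = 1,314 person-months per arm:
- Square-root form: 2(√0.27 − √0.216)√(1314/2) = 2 x 0.05486 x 25.63 = 2.812; Φ(2.812 − 1.960) = 80.3%.
- Log form: ln(0.27/0.216) = 0.2231; SE = √(1/354.8 + 1/283.8) = 0.0796; ratio 2.802; Φ(0.842) = 80.0%.

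The figure reproduces on 18 months, so the event rate is taken as given. The plan has no figure for the dose analyses.

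**3. Dose as adjuster.** Write log E(Y) = log t + α + βA + γD, with A = arm and D = minutes. A control has D = 0 and log rate α. A mentee with d minutes has α + β + γd. So exp(β) is the rate ratio at d = 0, and any effect delivered through calls sits in γ. The slope γ is learned only from non-randomised differences among mentees.

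**4. Dose as moderator.** For controls A x D = 0 = D; for mentees A x D = D. The columns are identical, and the matrix [1, A, D, A x D] has rank 3 of 4. A moderator term cannot be separated from a dose main effect.

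**5. Overlap.** Expected events are 0.27 x 3 = 0.81 in months 1-3 and 0.27 x 12 = 3.24 in 12 months. A quarter of the count (0.81/3.24) falls in the dose window.

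**6. Null simulation.** 100 per arm, 0.27 events per month, 12 months, no true effect, quasi-Poisson with log-time offset, 1,500 trials per row. Mentor and facility intercepts were left out. Assumptions not in the documents: about 70% of calls completed; each event in months 1-3 costs 0, 1 or 2 calls; gamma frailty variance (between-patient variation in rate) 0, 0.5 or 1; in the last two rows, completion is lower in frailer mentees (logit slope −0.5 on log frailty). Monte Carlo SE at 5% is √(0.05 x 0.95/1500) = 0.6 points.

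| Calls lost per event | Frailty variance | Arm RR given dose | Dose RR per 60 min | Dose rejected |
|---|---|---|---|---|
| 0 | 0 / 0.5 / 1 | 1.00 / 0.99 / 1.02 | 1.00 / 1.00 / 0.99 | 5.0 / 4.3 / 4.9% |
| 1 | 0 / 0.5 / 1 | 1.07 / 1.16 / 1.28 | 0.98 / 0.94 / 0.90 | 9.6 / 16 / 24% |
| 2 | 0 / 0.5 / 1 | 1.12 / 1.34 / 1.59 | 0.95 / 0.87 / 0.80 | 26 / 56 / 74% |
| 0, frailty-linked | 0.5 | 1.19 | 0.94 | 21% |
| 1, frailty-linked | 0.5 | 1.36 | 0.88 | 54% |

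The arm-only model held its level in all these rows (RR 0.99-1.00, rejection 4.2-5.6%). At 18 months, one call lost and variance 0.5, the arm RR was 1.13 and dose was rejected in 14%.

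A mediation reading splits the null into two false parts. With one call lost and variance 0.5, mean dose is 2.49 hours, so the indirect RR is 0.938^2.49 = 0.85. Multiplied by the direct RR of 1.16 this gives 0.99, close to the intention-to-treat RR of 1.00.

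**7. Sensitivity to how call-taking varies.** Section 6 rests on one assumed spread of engagement between mentees. With one week of calls lost per event and completion beta-distributed (mean 70%), the arm RR was 1.17 / 1.44 / 1.73 and dose was rejected in 21 / 37 / 56% at variance 0 / 0.5 / 1. With one completion probability for everyone, the arm RR ran from 1.62 to 5.31 and rejection from 47% to 95%. The direction is stable; the size is not.

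**8. Checking the remedy under the null.**
- Counting only months 4-12, one call lost per event: dose rejected in 5.4 / 7.6 / 15% at variance 0 / 0.5 / 1, and 36% with frailty-linked completion at 0.5. Under other spreads of engagement, with frailty present, the landmark alone rejected up to 98%.
- Within the intervention arm, landmark plus the months 1-3 event count: 4-7% when events alone reduce calls.
- The same, when frailer mentees also take fewer calls: 32-74% depending on the assumed strength and spread, falling to about 15-21% when baseline utilisation is added.

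**The case against.** The plan can be read more kindly. Section 4.1 already foresees exploratory analyses inside the intervention arm, and Section 9.4.9 pairs dose with concordance, which also has no meaning in controls. On a within-arm reading, steps 3 and 4 do not arise for Section 9.4.9. Section 6.4 only permits adjustment and names no model or endpoint. In mediation, an arm term net of the mediator is the direct effect that is sought, so it is not an error in itself. All of this stands, and it limits the point. It does not remove it: Section 9.4.9 speaks of the intervention's effect without restricting the population, Section 6.4 leaves the adjusted arm comparison open, and mediation still needs a time order and a confounder set.

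A reader might infer that admissions do cut call minutes, so that these analyses will give false results. The documents do not support that. None of their sections says so or gives a figure. Section 6.1.1 asks for at least four attempts a week and counts a 3-minute call as complete, and Section 6.1.2 adds in-person and video contact, so an admission need not cost a call. Average minutes per week has no stated denominator; averaging over weeks at home could weaken the link. On the other side, Section 5.1 selects patients with recent admissions, ED visits or missed treatments, and Section 7.1 lists severe illness as a reason for a mentee to stop, so reduced calling in sicker mentees is plausible.

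A reader might also infer that the primary result is at risk. It is not: mentees stay in their randomised arm whatever their dose.

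**Conclusion.** The concern holds in two parts of different strength. The structural part needs no assumption about behaviour: adjusting for dose changes the arm contrast to zero minutes versus usual care, and dose cannot be identified as a moderator of the arm effect. The bias part is conditional. If events or frailty reduce calls, dose analyses can show a false benefit of minutes and a false harm of arm under a null effect; if neither does, there is no inflation. The simulated sizes depend on assumed variation in engagement and event rate and should not be quoted as estimates for this trial. The affected analyses are optional or exploratory. The plan should still be changed, because the better specification is simple and the results are meant to inform scale-up.

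**What to change.** In Sections 6.4 and 9.4.9:
- Remove dose as an adjustment variable or moderator in the arm comparison.
- State that the dose analysis is confined to the intervention arm, consistent with Section 4.1.
- Fix dose at the end of month 3 and define the denominator of average minutes per week.
- Count only events after month 3, with log time after month 3 as offset.
- Adjust for the patient's months 1-3 event count and for baseline utilisation and risk.
- Label the result observational and non-causal, and say that residual confounding remains if sicker mentees take fewer calls. The specification should not be described as removing the bias.

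The cost is SAP wording; the plan already collects call records, monthly events and baseline utilisation. The downside is that the dose analysis loses the first 3 months of events and patients who leave before month 3.

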### 10 SUPPORTING DOCUMENTATION AND OPERATIONAL CONSIDERATIONS

#### 10.1 REGULATORY, ETHICAL, AND STUDY OVERSIGHT CONSIDERATIONS

##### 10.1.1 INFORMED CONSENT PROCESS

We will obtain informed consent from mentors and mentees separately. Recruitment procedures include screening for eligibility. Verbal consent will be provided by the participant for proceeding with screening. In some sites, a HIPAA consent form may be required prior to initiating any recruitment procedures, including screening for eligibility. We will comply with NIH Human Research Protections Program policies and procedures. The investigator will also comply with applicable regulatory requirements (45 CFR Part 46, 21 CFR Part 50, 21 CFR Part 56) and will adhere to the ICH-GCP. All of the informed documents are approved by the institutional review boards of each participating site.

##### 10.1.1.1 CONSENT/ASSENT AND OTHER INFORMATIONAL DOCUMENTS PROVIDED TO PARTICIPANTS

All documents, including recruitment scripts (in-person, virtual, phone or email/letter), will be IRB approved prior to use in this study. They will be available in English, and may be available in Spanish (site specific). Consent forms describing in detail the study intervention, study procedures, and risks will be given to the participant and written documentation of informed consent, or alterations in the procedure if IRB approved and described in the following section, will be completed prior to starting the study.

##### 10.1.1.2 CONSENT PROCEDURES AND DOCUMENTATION

Participants identified by the study recruitment strategies and who are deemed to be eligible for participation will provide informed consent. This may be performed according to local IRB approvals including the provision of written consent after an in-person discussion about the study with the research team. A copy of this written consent will be provided to the participant, stored in their research record, and many also be stored in their medical record, if required. Alterations of the consent process may also be performed if approved by local IRB. This may include a virtual research consent visit where the participant and study team have a video visit to discuss the study. The consent form will be provided ahead of time to the participant by mail, email (if provided by the participant and requested) or picked up at a clinic location if permitted. The patient may then return a signed copy of the consent to the research team. It will be stored as above. A phone consent process may also be performed similar to a virtual consent visit. A final option may be the execution of an electronic version of the consent form through RedCap. In this case, the participant will still have either a phone or virtual visit with the

coordinator to discuss the study. In place of a paper copy of the consent form, an electronic exact content copy will be sent to the patient by email link for their review and electronic signature. This will be stored in RedCap. A copy will be printed, if possible, and stored in the participant's research file and/or medical record if required. Study materials may provide a web address or QR code to the study's econsent if permitted by local IRB. Consent forms will be available in English, and may be available additionally in Spanish (site specific).

All participants currently active in the study after 4/30 amendment approval, and any new enrollments, will execute the revised version of the informed consent document describing the revised study timeline.

#### 10.1.2 STUDY DISCONTINUATION AND CLOSURE

This study may be temporarily suspended or prematurely terminated if there is sufficient reasonable cause. Written notification, documenting the reason for study suspension or termination, will be provided by the suspending or terminating party to study participants, investigator, funding agency, and regulatory authorities. If the study is prematurely terminated or suspended, the Principal Investigator (PI) will promptly inform study participants, the Institutional Review Board (IRB), and sponsor/funding agency and will provide the reason(s) for the termination or suspension. Study participants will be contacted, as applicable, and be informed of changes to study visit schedule.

Circumstances that may warrant termination or suspension include, but are not limited to:

- Determination of unexpected, significant, or unacceptable risk to participants
- Insufficient compliance to protocol requirements
- Data that are not sufficiently complete and/or evaluable
- Unforeseen circumstances, including natural disasters, that preclude safe execution of study activities

The study may resume once concerns about safety, protocol compliance, and data quality are addressed, and satisfy the funding agency, sponsor, or other relevant regulatory or oversight bodies (DSMB).

#### 10.1.3 CONFIDENTIALITY AND PRIVACY

Participant confidentiality and privacy is strictly held in trust by the participating investigators, their staff, the safety and oversight monitor(s), and the sponsor(s) and funding agency. This confidentiality is extended to the data being collected as part of this study. Data that could be used to identify a specific study participant will be held in strict confidence within the research team. No personally-identifiable information from the study will be released to any unauthorized third party without prior written approval of the sponsor/funding agency.

All research activities will be conducted in as private a setting as possible. The study monitor, other authorized representatives of the sponsor or funding agency, representatives of the Institutional Review Board (IRB), or regulatory agencies, may inspect all documents and records required to be maintained by the investigator, including but not limited to, medical records for the participants in this study. The clinical study site will permit access to such records.

The study participant's contact information will be securely stored at each clinical site for internal use during the study. At the end of the study, all records will continue to be kept in a secure location for as long a period as dictated by the reviewing IRB, Institutional policies, or sponsor/funding agency requirements.

Study participant research data, which is for purposes of statistical analysis and scientific reporting, will be transmitted to and stored at the study data coordinating center. This will not include the participant's contact or identifying information. Rather, individual participants and their research data will be identified by a unique study identification number. The study data entry and study management systems used by study sites will be secured and password protected. At the end of the study, all study databases will be de-identified and archived at the data coordinating center, and shared with data repositories or other investigators as may be required or agreed upon for additional research.

#### *Measures Taken to Ensure Confidentiality of Data Shared per the NIH Data Sharing Policies*

It is NIH policy that the results and accomplishments of the activities that it funds should be made available to the public (see <https://grants.nih.gov/policy/sharing.htm>). The PI will ensure all mechanisms used to share data will include proper plans and safeguards for the protection of privacy, confidentiality, and security for data dissemination and reuse (e.g., all data will be thoroughly de-identified and will not be traceable to a specific study participant). Plans for archiving and long-term preservation of the data will be implemented, as appropriate.

#### *Certificate of Confidentiality*

To further protect the privacy of study participants, the Secretary, Health and Human Services (HHS), has issued a Certificate of Confidentiality (CoC) to all researchers engaged in biomedical, behavioral, clinical or other human subjects research funded wholly or in part by the federal government. Recipients of NIH funding for human subjects research are required to protect identifiable research information from forced disclosure per the terms of the NIH Policy (see <https://humansubjects.nih.gov/coc/index>). As set forth in 45 CFR Part 75.303(a) and NIHGPS Chapter 8.3, recipients conducting NIH-supported research covered by this Policy are required to establish and maintain effective internal controls (e.g., policies and procedures) that provide reasonable assurance that the award is managed in compliance with Federal statutes, regulations, and the terms and conditions of award. It is the NIH policy that investigators and others who have access to research records will not disclose identifying information except when the participant consents or in certain instances when federal, state, or local law or regulation requires disclosure. NIH expects investigators to inform research participants of the protections and the limits to protections provided by a Certificate issued by this Policy.

---

